
C. RESEARCH DESIGN AND METHODS

Study Type/Design

This is an open label safety and feasibility trial using Acthar® in addition to our center-specific standard therapy, which could include increase in maintenance immunosuppression, high dose IVIG (2 g/Kg), and/or Rituximab, in patients with CAMR.

The inclusion criteria include:

- Age >18 years
- Morphologic diagnosis of CAMR, by light &/or electron microscopy any time after transplantation
- eGFR>25 ml/min

The exclusion criteria include:

- Diagnosis of malignancy within a year prior to enrollment (except cured cutaneous basal cell or squamous cell carcinoma).
- Lack of evidence of antibody involvement
- Pregnancy, lactation, or refusal to use birth control in women of child bearing potential
- Active infection, or history of HIV
- History of liver or thoracic transplant

Endpoints

The **efficacy primary endpoint** of the study is the composite of graft loss, death, decrease in eGFR>10%, and increase in proteinuria, defined by >50% increase if baseline proteinuria <2 g, or persistence of proteinuria >2 g otherwise, at one year after initiation of the treatment. The **safety endpoints** include the serious adverse events during the study period attributable to study drug.

Secondary end-points:

- 1- Death
- 2- Graft loss (defined as return to dialysis or retransplantation)
- 3- Decrease in eGFR>10% at 1 year
- 4- Increase in proteinuria >50% if baseline proteinuria<2 g, or persistence of proteinuria >2 g otherwise
- 5- Persistence of DSA, by number of antibodies and related MFI
- 6- g and cg scores in the biopsies, maximum number of glomerular CD68+ cells; severity of interstitial fibrosis/tubular atrophy

Patient Recruitment

The study will be conducted in renal transplant recipients with histological diagnosis of chronic AMR at any time after transplantation with fairly preserved graft function. We are planning to enroll 20 patients with histological diagnosis of CAMR.

Treatment Overview Screening protocol, concomitant treatments, etc.

Dosage and Administration of Acthar

Subjects will receive Acthar® 40 units twice a week subcutaneously for 2 weeks. If the drug is well tolerated the dose will be increased to 80 units twice a week for another 22 weeks.

Dosage considerations in special circumstances, and based on the side effect profile of individual participants, the investigator may recommend a modified dose Acthar® as indicated below:

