- 1) Patients with diabetes may be given Acthar® 16 units daily, instead of 80 units twice a week (with the aim of maintaining better glycemic control (Tumlin 2013))
- 2) Patients who develop side effects on the standard dose of Acthar® (40 units twice a week followed by 80 units twice a week) may be given a lower, tolerable dose of Acthar® either on a daily or a twice a week basis.

The patients will be maintained on their center-specific standard maintenance regimen, typically consisting of Tacrolimus,

Mycophenolate Mofetil/Sodium, and prednisone.

Patient Monitoring and Evaluation /Laboratory Testing and Study Schedule

After screening for the inclusion/exclusion criteria, the patients will be consented and enrolled in the study. The initial visit and subsequent study-related visits at 2, 4, 8, 12, 24, 36 and 52 weeks will include routine evaluation and physical examination and laboratory studies including CBC, electrolyte panel, eGFR, albumin, liver enzymes, and CNI/Sirulimus drug level, according to the center's standard of care. DSA will be tested at week 24, and 52 and patients will undergo a biopsy at week 52, as a part of our standard of care. The biopsies will be evaluated by light and electron microscopy using standard histological Banff criteria, and staining for CD68.

Potential Pitfalls and Contingencies Describe plans to address possible problems

We do not expect major problems with the treatment. It is not clear if treatment with Acthar will prevent or slow down the progression of CAMR. However, since there is no alternative therapy available, lack of response will not change the course of the disease process. There is a possibility that the patients could develop hyperglycemia; if so appropriate therapy will be provided.

Data Processing and Analysis

Statistical /Analytical Plan

The data will be collected on the variables listed above. Standard statistical methods will be used for description of primary and secondary endpoints. As a secondary analysis a historical cohort of patients with CAMR will be identified and graft survival in the study group will be compared with the historical cohort using survival analysis methods.

Sample Size Justification

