The enrollment plan is not based on power calculation, as there is no previously successful treatment reported to use for sample size calculation. This is a cohort of reasonable size that is expected to provide invaluable data regarding the treatment effect, and provide data for power calculation for future studies.

D. REGULATORY, SAFETY AND MONITORING

After the initial visit the subsequent study-related visits will occur at 2, 4, 8, 12, 24, 36 and 52 weeks and will include routine evaluation and physical examination and laboratory studies as noted above for evaluation for efficacy and safety endpoints. The adverse effects will be reported to IRB and the sponsor, and patients with serious adverse effects resulting from the study drug, not amenable to medical therapy and those non-compliant with study protocol will be removed from the study. IND will be file with the FDA if the IRB requires it. The study protocol will be registered with Clinical trials.com

E. ESTIMATED DURATION OF THE STUDY AND CRITICAL TIMELINE ELEMENTS

I. Please complete expected/estimated dates:

| Table 1: Critical Timeline Elements | |
|--|-------------------|
| Element Name | Date |
| IRB approval, expected | 4-6 weeks |
| IND submission, expected | 6 weeks |
| Study start date, estimated | April 1, 2015 |
| Enrollment completion date, estimated | December 31, 2020 |
| Study completion date, estimated | December 31, 2021 |

II. Describe publication plan and anticipated number of abstracts and manuscript submissions (include intended conference(s) for presentation and month, year of conference(s)):

At one year and 2 years the interim analysis will be performed and the results will be submitted to national/international nephrology/transplant meetings, and at the completion of the study the final results will be submitted in the form of a primary manuscript reporting the primary efficacy and safety data, and secondary manuscripts reporting different secondary endpoints, as appropriate.

F. REFERENCES

R Ugarte, B. Kiangkitiwan, A. Haririan. Antibody-mediated rejection in kidney transplantation. 2014. 281-300. In M. Weir, E. Lerma (editors): *Kidney Transplantation, Practical Guide to Management*. Springer

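### Removal from the study for unmanageable toxicity or non-compliance is not separated from the end of outcome collection, so one-year results could be informatively incomplete

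*Combined protocol and SAP*

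**What the plan says.** **Removal.** Section D (Regulatory, Safety and Monitoring) names two groups in one sentence: patients with serious adverse effects of the study drug "not amenable to medical therapy and those non-compliant with study protocol will be removed from the study". The sentence has no time limit, and its paragraph covers visits up to week 52. Non-compliance is not defined.

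**Endpoints (section C, Endpoints).** The efficacy composite is judged "at one year after initiation of the treatment". The safety endpoint is "the serious adverse events during the study period attributable to study drug".

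**Schedule (section C).** After 2 weeks at the starting dose, the dosing text reads: "If the drug is well tolerated the dose will be increased to 80 units twice a week for another 22 weeks". Patients who develop side effects "may be given a lower, tolerable dose of Acthar". Follow-up consists of "study-related visits at 2, 4, 8, 12, 24, 36 and 52 weeks", and "DSA will be tested at week 24, and 52 and patients will undergo a biopsy at week 52".

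**Analysis (section C, Statistical/Analytical Plan).** Endpoints are to be described by usual methods, and "graft survival in the study group will be compared with the historical cohort using survival analysis methods". The documents contain no statement on follow-up after removal, the analysis set, censoring or a missing week 52 outcome. No redaction or gap in the text appears at these places.

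**The concern.** Stopping a drug and leaving a study are different events. Section D uses a single phrase that, on its plain words, means the second. Both triggers arise after treatment starts, and both may be related to how the graft fares. If these patients drop out of the data, those who remain at one year are a selected group.

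Four results are exposed:
- the one-year composite;
- the week 52 donor-specific antibody (DSA) test and biopsy;
- safety data after removal, which matter in what section C calls a safety and feasibility trial;
- the comparison with historical patients, if removed patients are censored.

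The Sample Size Justification also says that the results should inform power calculations for later studies, so a selected estimate would carry forward.

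**Working it through.** The plan gives no removal rate, dropout allowance or expected event rate, and says that its 20 patients do not come from a power calculation. There is no figure to reproduce. The counts of removed patients and the 10 of 20 result below are assumptions, used only for scale.

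**Step 1. When scheduled dosing ends.** From the dosing text, 2 + 22 = 24 weeks. Follow-up runs to week 52, so 52 − 24 = 28 weeks, or 28/52 = 53.8% of the year, come after dosing on the standard schedule. The lower-dose option states no duration of its own.

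**Step 2. Three readings of removal, set against that schedule.**
- *End of follow-up.* This fits the words at any time up to week 52. Later outcomes are not collected.
- *Stopping drug only.* This fits up to week 24. It does not fit a patient found non-compliant at week 36, who has no scheduled drug left to stop.
- *Exclusion from the reported cohort.* This is possible at any time. It still selects patients on events after baseline.

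The first and third readings make the results selective. The second would not, but it does not cover the whole period over which the sentence applies.

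**Step 3. What is lost if removal ends follow-up.** There are 7 follow-up visits (weeks 2, 4, 8, 12, 24, 36, 52), DSA tests at weeks 24 and 52, and one scheduled follow-up biopsy at week 52.

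| Removed just after | Visits lost | DSA tests lost | Biopsy lost | Weeks lost |
|---|---|---|---|---|
| week 12 | 3 of 7 (24, 36, 52) | 2 of 2 | 1 of 1 | 52 − 12 = 40 |
| week 24 | 2 of 7 (36, 52) | 1 of 2 | 1 of 1 | 52 − 24 = 28 |

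Of the 40 weeks lost after week 12, 24 − 12 = 12 are scheduled dosing weeks and 28 follow dosing.

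**Step 4. Range from unknown outcomes.** With x events among patients of known status and k unknown, the one-year proportion lies between x/20 and (x + k)/20. The width is k/20: 5, 10, 15 or 20 percentage points for k = 1, 2, 3 or 4. This applies only where composite status is wholly unknown. A death or graft loss recorded before removal already settles it.

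**Step 5. Effect of analysing only those who remain.** Assume that the full result would be 10/20 = 50%.
- Two removed: 8/18 = 44.4% if both had events, 10/18 = 55.6% if neither did.
- Four removed: 6/16 = 37.5% if all had events, 10/16 = 62.5% if none did.

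**Step 6. Sampling error for comparison.** The exact (Clopper-Pearson) 95% interval for 10/20 runs from the 2.5% quantile of Beta(10, 11) to the 97.5% quantile of Beta(11, 10): 27.2% to 72.8%. Its width is 72.8 − 27.2 = 45.6 points, more than twice the 20-point range for four unknown patients.

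**The case against.** The strongest reply is that this is a small, uncontrolled, descriptive pilot in which few patients may be removed and much of the data would exist anyway. Several parts of it stand.

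- *Few removals for toxicity.* A lower dose is allowed for side effects, and removal requires a serious effect that medical therapy cannot manage. This may keep the first group small. It does nothing for the non-compliant group or for follow-up after removal.
- *Standard-of-care data.* The DSA tests, biopsy and visit laboratory work are described as standard of care, so some results may be retrievable. The plan does not say that they would be collected or used after removal. Urine protein, which the composite needs, is not named in the visit laboratory list. That list is introduced as non-exhaustive, so urine testing may be intended, but complete retrieval is not assured.
- *Missed visits.* If late non-compliance means not attending, those data are lost under any rule. This is true for those patients, and it is why missing outcomes need reporting as well as preventing.
- *Sampling error is larger.* This is correct (step 6). A confidence interval does not, however, account for selective loss.
- *Unstated censoring.* The absence of a censoring rule for the historical cohort is a separate gap that would exist without the removal sentence.

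A reader might infer that removal can only mean the end of follow-up, because a patient at week 36 has no drug left to stop. The documents do not support that: exclusion from the reported cohort is also open. What they support is an ambiguity in which the drug-only reading fits only part of the period.

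**Conclusion.** The concern holds as a minor point. A stated rule, taken literally, ends outcome collection for patients selected by toxicity or adherence after baseline, and nothing elsewhere in the documents offsets it. The alternative readings either do not fit removal after week 24 or also select patients on post-baseline events.

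The size is 5 percentage points of best/worst-case range per patient of wholly unknown status, in a trial of 20 whose sampling error is already wide. This assumes 20 treated patients and that removal ends data collection. How many would be removed is unknown.

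Two stronger inferences should be resisted. One is that the results would favour the drug: the documents give no data linking removal to outcome, so neither the direction nor the size of bias can be fixed. The other is that serious toxicity would go unrecorded: section D requires adverse effects to be reported, so the event that triggers removal is still reportable. Only what happens afterwards is at risk.

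**What to change.** Leave the clinical rules for stopping or changing study drug to the sponsor, and ask the sponsor to state in section D what removal means. Then add the following.

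- **Section D:** whatever happens to study drug, every patient who received at least one dose stays in outcome and safety data collection at the visits already scheduled to week 52, unless consent is withdrawn. This includes the eGFR and proteinuria needed for the composite.
- **Statistical/Analytical Plan:** all treated patients are analysed, and graft survival is not censored at removal, at stopping drug or at non-compliance.
- **Statistical/Analytical Plan:** the number of patients with missing week 52 status and the reasons are reported, with best- and worst-case bounds for the composite.

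The cost is a few sentences and some tracing effort, with no visits added to the schedule. A urine protein measurement may have to be added, since the laboratory list does not name one. Some non-compliant patients will still miss visits. The estimate will include time off drug and may look less favourable.
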